4.2 Delayed hypersensitivity reactions

In case of late-occurring hypersensitivity symptoms (e.g., appearance within one week after treatment of a localized or generalized pruritis), symptomatic treatment may be given (e.g., oral antihistamine or corticosteroids).

4.3 Treatment of \geq Grade III Autoimmune Adverse Events

For **skin-related** \geq Grade III autoimmune toxicity, including severe generalized pruritis or rash, symptomatic treatment will be given. The types of therapy may include local skin care, antihistamines, or corticosteroids (which can be local/topical or systemic) as clinically indicated. At the discretion of the principal investigator, patients experiencing a skin-related autoimmune toxicity \geq Grade III who have not required systemic steroids may resume MDX-010 once the skin symptoms improve (see Section 3.3.1). Patients who require systemic steroid therapy will not receive further treatments with MDX-010.

Treatment for **non-skin-related** autoimmune adverse events \geq Grade III will be prescribed as clinically indicated depending on the severity of the symptoms and/or physical manifestations. Treatment may include oral, locally-delivered (e.g., per rectum) or i.v. steroids and/or other supportive care. No further doses of MDX-010 will be given once a patient develops a \geq Grade III non-skin-related autoimmune adverse event attributable to the investigational agents or if the patient requires systemic steroid therapy.

4.4 Treatment of \geq Grade III Non-autoimmune-mediated Adverse Events

Treatment for any \geq Grade III adverse event not felt to be due to an autoimmune process may be treated as clinically indicated. No further doses of MDX-010 will be given once a patient experiences a non-skin-related \geq Grade III adverse event attributable to the investigational agents.

4.5 Treatment of Any Ocular Toxicity

Patients who report any visual symptom will be immediately referred to an ophthalmologist. Upon evaluation by the ophthalmologist, the patient will be treated as deemed appropriate by the ophthalmologist, including peri-ocular steroid injections or steroid eyedrops if necessary. No further doses of MDX-010 will be given once a patient experiences an autoimmune ocular toxicity attributable to the investigational agents.

5.0 Data Collection and Evaluation

5.1 Data Collection

Investigators or designee must enter the information required by the protocol onto the Medarex Case Report Forms (CRFs). Medarex monitors, or their designee, will review the CRFs for completeness and accuracy, and instruct site personnel to make any required corrections and/or additions. Once the CRFs are completed and all queries are resolved they will be placed in a Medarex central database for data management.

Data items from the CRFs will be entered into the study database using electronic data capture. The information entered into the database will be systematically checked using error messages printed from validation programs and database listings. Errors or omissions will be queried and returned to the investigational site for resolution. Quality control audits of the database will be made after entering data from each visit.

Concomitant medications, coexistent diseases and adverse events will be appropriately coded.

When the database has been declared to be complete and accurate, the database will be locked. Any changes to the database after that time will only be made by joint written agreement between the Medarex Clinical Trial Leader, the Trial Statistician and the Data Manager.

5.2 Data Safety and Monitoring Plan

Careful evaluation to ascertain the toxicity and anti-tumor efficacy of therapy will be performed. The principal investigator will monitor the data and toxicities to identify

trends. The principal investigator will be responsible for revising the protocol as needed to maintain safety. The NCI IRB will review submitted adverse events monthly to also evaluate trends and will require a follow up plan from the principal investigator whenever a trend is identified.

5.3 Response Criteria:

5.3.1 Clinical Response

5.3.1.1 Evaluation of target lesions¹

Complete Response (CR):	Disappearance of all target lesions
Partial Response (PR):	At least a 30% decrease in the sum of the longest diameter (LD) of target lesions taking as reference the baseline sum LD.
Progression (PD):	At least a 20% increase in the sum of LD of target lesions taking as reference the smallest sum LD recorded since the treatment started or the appearance of one or more new lesions.
Stable Disease (SD):	Neither sufficient shrinkage to qualify for PR nor sufficient increase to qualify for PD taking as references the smallest sum LD.

5.3.1.2 Evaluation of non-target lesions²

Complete Response (CR):	Disappearance of all non-target lesions and normalization of tumor marker level.
Non-Complete Response:	Persistence of one or more non-target lesions
Progression (PD):	Appearance of one or more new lesions. Unequivocal progression of existing non-target lesions.

5.3.1.3 Evaluation of best overall response

The best overall response is the best response recorded from the start of the treatment until disease progression/recurrence (taking as reference for progressive disease the smallest measurements recorded since the treatment started). The patient's best response assignment will depend on the achievement of both measurement and confirmation criteria.

¹ All measurable lesions up to a maximum of 10 lesions representative of all involved organs should be identified as **target lesions** and recorded and measured at baseline. Target lesions should be selected on the basis of their size (lesions with the longest diameter) and their suitability for accurate repetitive measurements (either by imaging techniques or clinically). A sum of the longest diameter (LD) for all target lesions will be calculated and reported as the baseline sum LD. The baseline sum LD will be used as reference to further characterize the objective tumor response of the measurable dimension of the disease.

² All other lesions (or sites of disease) should be identified as **non-target lesions** and should also be recorded at baseline. Measurements are not required, and these lesions should be followed as "present" or "absent."

Target Lesions	Non-Target Lesions	New Lesions	Overall Response
CR	CR	No	CR
CR	Non-CR/Non-PD	No	PR
PR	Non-PD	No	PR
SD	Non-PD	No	SD
PD	Any	Yes or No	PD
Any	PD	Yes or No	PD
Any	Any	Yes	PD

5.3.1.4 Confirmatory Measurement/Duration of Response

Confirmation

To be assigned a status of PR or CR, changes in tumor measurements must be confirmed by repeat studies that should be performed at least 4 weeks after the criteria for response are first met. In the case of SD, follow-up measurements must have met the SD criteria at least once after study entry at a minimum interval of 6-8 weeks.

5.3.1.5 Duration of overall response

The duration of overall response is measured from the time measurement criteria are met for CR/PR (whichever is first recorded) until the first date that recurrent or progressive disease is objectively documented (taking as reference for progressive disease the smallest measurements recorded since the treatment started).

The duration of overall complete response is measured from the time measurement criteria are first met for CR until the first date that recurrent disease is objectively documented.

5.3.1.6 Duration of stable disease

Stable disease is measured from the start of the treatment until the criteria for progression are met, taking as reference the smallest measurements recorded since the treatment started.

5.4 Toxicity Criteria:

Information about all adverse events, whether volunteered by the patient, discovered by investigator questioning, or detected through physical examination, laboratory test or other means, will be collected and recorded on the Adverse Event Case Report Form and followed, as appropriate. An adverse event is any undesirable sign, symptom or medical condition occurring after starting study treatment, even if the experience is not considered to be treatment-related.

Medical conditions/diseases present before starting study treatment are only considered adverse events if they worsen after starting study treatment. Clinical experiences occurring

before starting study treatment but after signing the informed consent form are recorded on the Medical History/Current Medical Conditions Case Report Form. Abnormal laboratory values or test results inducing clinical signs or symptoms are recorded on the Adverse Events Case Report Form under the signs, symptoms or diagnoses associated with them.

As far as possible, each adverse event will also be described by: its duration (start and end dates), the severity grade (Cancer Therapy Evaluation Program Common Toxicity Criteria, CTC AE 3.0, located on the internet at <http://ctep.cancer.gov/reporting/ctc.html>) and its relationship to treatment (unrelated/unlikely/possible/probable/definite), and the action(s) taken.

Serious adverse events

Information about all serious adverse events will be collected and recorded on the Serious Adverse Event Report Form. To ensure patient safety, each of such serious adverse events must also be reported to Medarex within 24 hours of learning of its occurrence.

A serious adverse event is defined in general as an untoward (unfavorable) experience which:

- Is fatal or life-threatening,
- Requires or prolongs hospitalization,
- Is significantly or permanently disabling or incapacitating,
- Constitutes a congenital anomaly or a birth defect,
- Jeopardizes the patient and may require medical or surgical intervention to prevent one of the outcomes listed above
- Is \geq grade 4 severity hematological adverse event
- Is \geq grade 3 severity non-hematological adverse event
- Is \geq grade 3 severity infusion adverse event (occurring \leq 24 hours after start of infusion)

Events not considered to be serious adverse events are: hospitalizations occurring under the following circumstances--planned before entry into the clinical study, for elective treatment of a condition unrelated to the studied indication or its treatment, or part of the normal treatment or monitoring of the studied indication and not associated with any deterioration in condition; events occurring on an emergency, outpatient basis that do not result in admission (unless fulfilling the criteria above).

This study will utilize the CTC AE 3.0 for toxicity and adverse event reporting. A copy of the CTC AE 3.0 can be downloaded from the CTEP web site: <http://ctep.cancer.gov/reporting/ctc.html>. All appropriate treatment areas should have access to a copy of the CTC AE 3.0.

5.5 Statistical Section:

[figure not shown]
The primary objective of this study is to determine whether single agent MDX-010 antibody is able to result in clinical responses (PR or CR) in patients with stage IV pancreatic cancer. Our experience with MDX-010 in the melanoma and renal cell population has shown a correlation between autoimmune toxicity and tumor response.

For each of the two groups, this trial will be conducted as a Phase II clinical trial using an optimal design [REDACTED] The trial will seek

to rule out an undesirably low response probability of 5% ($p_0=0.05$) in favor of a level which demonstrates potentially useful activity of 20% ($p_1=0.20$). With an $\alpha=0.05$ (5% probability of accepting a poor combination, and $\beta=0.10$ (10% probability of rejecting a good combination), initially 21 patients will be enrolled. If 0-1 of 21 have a clinical response as defined in section 5.3, then accrual will stop and we will conclude that the combination is not sufficiently active in the disease being studied. If 2+/21 patients respond, then accrual will continue until 41 patients have been enrolled. If 2-4 of 41 respond, this will be insufficient activity to warrant further evaluation. If 5+/41 have documented clinical responses, the agent will be considered active in pancreatic carcinoma. Under this design if the null hypothesis were true (5% true response probability), there is a 72% probability of early termination.

It is expected that it will require 2-4 years to accrue up to 82 evaluable patients.

6.0 Human Subjects Protections

6.2 Participation of children

Minors will not be treated in this study.

6.3 Evaluation of Benefits and Risks/Discomforts

The patients to be entered in this protocol have locally advanced and metastatic cancer and limited life expectancies. The experimental treatment has a chance to provide clinical benefit though this is unknown. All possible benefits and risks will be carefully explained to all patients and informed consent documents will be signed by the patient prior to entrance into the protocol.

6.4 Consent and assent processes and documentation

All patients are thoroughly screened prior to admission onto this study. During this time, the patient, along with family members, will be presented with a detailed description of the protocol treatment. The specific requirements, objectives, advantages and disadvantages will be presented. The Informed Consent document is given to the patient and they are asked to review it and ask questions prior to agreeing to participate in this protocol. The patient is reassured that participation on this trial is entirely voluntary and

that they can withdraw or decide against treatment at any time without adverse consequences. The Principal Investigator, senior physician, research nurse or medical staff fellow under the supervision of the PI is responsible for completing the consent process and a copy of the consent is offered to the patient.

7.0 Data Reporting

7.1 Definition of serious adverse events

A serious adverse event is defined as an untoward (unfavorable) experience, which meets any of the following criteria:

- Is fatal or life-threatening
- Requires or prolongs hospitalization
- Is significantly or permanently disabling or incapacitating
- Constitutes a congenital anomaly or a birth defect
- Jeopardizes the patient and may require medical or surgical intervention to prevent one of the outcomes listed above

7.2 Reporting responsibility

Any serious adverse event occurring in a patient after providing informed consent, while receiving study treatment, and until four (4) weeks after stopping study treatment must be reported. The period after discontinuing study treatment may be extended if there is a strong suspicion that the drug has not yet been eliminated. All serious adverse events must also be reported for the period in which the study interferes with the standard medical treatment given to a patient (e.g. treatment withdrawal during washout period, change in treatment to a fixed dose of concomitant medication).

Each serious adverse event must be reported by the investigator to Medarex within 24 hours of learning of its occurrence, even if it is not treatment-related. Each serious adverse event must also be reported to NCI IRB. The NCI AE form will be used for submitting adverse events on this study within 24 hours to the NCI IRB e-mail address, with a written report to follow in 10 working days.

Follow-up information about a previously reported serious adverse event must also be reported to Medarex. If the serious adverse event has not been previously documented (new occurrence) and it is thought to be related to study drug, an investigator alert, to inform all investigators involved in any study with the same drug that this serious adverse event has been reported, may be issued.

7.3 Reporting procedures

The investigator must complete the Serious Adverse Event Report Form in English. Serious adverse events are graded using the Cancer Therapy Evaluation Program Common Toxicity Criteria, CTC AE 3.0, located on the Internet at <http://ctep.cancer.gov/reporting/ctc.html>. Adverse events not included in the Cancer Therapy Evaluation Program Common Toxicity Criteria, CTC AE 3.0 must be reported according to the definitions in Section 7.4.

The investigator must report serious event information to the NCI IRB and Medarex and send a completed SAE form by facsimile transmission within 24 hours to the NCI IRB and Medarex [REDACTED] or their designee.

Follow-up information is sent to the same person to whom the original Serious Adverse Event Form was sent, re-stating the date of the original report. Either a new Serious Adverse Event Form is sent (stating that this is a follow-up), or the original one resent (with the new information highlighted and a new date provided). The follow-up must describe whether the experience has resolved or continues, if and how it was treated, and whether the patient continued or discontinued study participation. The form and facsimile transmission confirmation sheet must be retained.

Contact persons and numbers - The telephone and facsimile transmission numbers of study related personnel are listed in the investigator folder provided for each individual site.

Questions referring to a specific serious adverse event occurring in a study patient should be directed to the local clinical development contact person or as specified in the investigator folder provided for the site. Questions concerning the facsimile transmission of a Serious Adverse Event Form should be directed to Medarex or their designee.

7.4 Instructions for completing adverse event case report form

Adverse event: Any unfavorable symptom, sign, or disease (excluding an abnormal laboratory finding) temporally associated with the use of a medical treatment or procedure that may or may not be considered related to the medical treatment or procedure. Syndromes, when diagnosed by a physician, are reported as adverse events.

Each adverse event is to be reported on an Adverse Event Case Report Form. As far as possible, each adverse event must also be described by:

- Its duration (start and end dates)
- Its severity grade its relationship to treatment
- Its relationship to treatment
- The action(s) taken

Adverse events are graded using the Cancer Therapy Evaluation Program Common Toxicity Criteria, CTC AE 3.0 (located on the Internet at <http://ctep.cancer.gov/reporting/ctc.html>). Adverse events not included in the Cancer Therapy Evaluation Program Common Toxicity Criteria, CTC AE 3.0 must be reported and graded according to the definitions provided below.

General grade definitions for severity of adverse events	
Grade	Quality
0	No adverse event or within normal limits
1	Mild adverse event
2	Moderate adverse event
3	Severe undesirable adverse event
4	Life threatening or disabling adverse event

5	Death related to adverse event
---	--------------------------------

Attribution of adverse event: Assign attribution of each adverse event using the criteria provided in the table below.

General definitions for attribution of adverse events		
Code	Descriptor	Definition
5	Definite	The adverse event is clearly related to the investigational agent(s)
4	Probable	The adverse event is likely related to the investigational agent(s)
3	Possible	The adverse event is possibly related to the investigational agent(s)
2	Unlikely	The adverse event is doubtfully related to the investigational agent(s)
1	Unrelated	The adverse event is clearly not related to the investigational agent(s)

Action(s) taken: Assign actions taken in response to an adverse event using the criteria provided in the table below.

General definitions for actions taken in response to an adverse event	
Code	Action
0	No action taken
1	Study drug dosage adjusted / temporarily interrupted
2	Study drug permanently discontinued due to this adverse event
3	Concomitant medication taken
4	Non-drug therapy given
5	Hospitalization / prolonged hospitalization

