5.9.3 Clinical Laboratory Tests

Clinical laboratory test values outside the normal range will be flagged in the data listing.

Laboratory data (hematology, biochemistry, urinalysis, pregnancy test, antinuclear antibody (ANA), autoimmune panel, antithyroglobulin, thyroid function tests, etc.) will be

summarized by group for scheduled visits based on individual visit values as well as change from baseline. Shift tables from baseline to post-baseline visits will also be presented.

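### Protocol 5.4 and 7.4 disagree on whether a laboratory abnormality is an adverse event, so symptom-free severe laboratory toxicity may be recorded inconsistently and under-counted

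*Protocol*

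**What the plan says.** Protocol 7.4 (instructions for the adverse event form) gives this definition: "Any unfavorable symptom, sign, or disease (excluding an abnormal laboratory finding) temporally associated with the use of a medical treatment". The words "excluding an abnormal laboratory finding" carry no exception for grade, seriousness or clinical significance. Section 7.4 does keep diseases, and syndromes that a physician has diagnosed, as adverse events.

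Protocol 5.4 (Toxicity Criteria) covers the same form and says that information on adverse events "detected through physical examination, laboratory test or other means, will be collected and recorded on the Adverse Event Case Report Form". It has one explicit sentence on laboratory values: "Abnormal laboratory values or test results inducing clinical signs or symptoms are recorded on the Adverse Events Case Report Form", under the associated sign, symptom or diagnosis. Its list of serious events includes any event of at least "grade 4 severity hematological adverse event", and non-hematological events of grade 3 or higher. Grading is by CTC AE 3.0.

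Protocol 7.1 defines a serious event by five outcome criteria and omits the grade criteria of 5.4.

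SAP 5.9.1 builds the adverse event tables from events as the investigator documented them. SAP 5.9.3 handles laboratory data separately, with visit values, change from baseline, shift tables and a flag: "Clinical laboratory test values outside the normal range will be flagged in the data listing". It mentions no toxicity grade and does not define the shift categories. The SAP also states that efficacy will not be analyzed.

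**The concern.** Two sections give sites different rules for one form. Blood counts and chemistry are measured before each later dose and again after each course, so severe abnormalities without symptoms will be detected if they occur. Whether they then become adverse events depends on which section the site follows.

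What is at stake is the SAP's main remaining output. With efficacy dropped, the counts of grade 3 or above and serious adverse events carry the report. An event that 7.4 keeps off the form cannot reach a table built from the form, and the laboratory tables are not specified to show its severity. Omission can only lower those counts.

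**Working it through.** No sample size, power or alpha figure is in question, so the check is a comparison of the text followed by an illustration of scale.

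**Step 1. Follow three kinds of laboratory abnormality through the rules.**

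| Case | Protocol 7.4 | Protocol 5.4 | Reaches the adverse event tables? |
|---|---|---|---|
| A. Causes signs or symptoms | The symptom or sign is an adverse event | Recorded under the sign, symptom or diagnosis | Yes |
| B. Leads to a diagnosed disease or syndrome | Adverse event | Recorded under the diagnosis if it caused signs or symptoms; otherwise open to recording as a medical condition found by laboratory test | Yes |
| C. Isolated, symptom-free, grade 3-4 | Excluded | Can be recorded under the general collection sentence; if recorded, serious by grade (hematological grade 4, non-hematological grade 3 or higher) | Only if the site followed 5.4 |

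The conflict is confined to case C. Neither section is stated to take precedence.

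**Step 2. Compare the definitions of a serious event.** For a case C event, 5.4 makes grade alone sufficient. Under 7.1 the event is serious only if one of the five outcome criteria is met. The same finding can thus be serious under 5.4, not serious under 7.1 and not an adverse event under 7.4.

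**Step 3. Look for signs of the protocol's intent.** Protocol 3.3.1 has to exempt autoantibody detection without symptoms from its autoimmune toxicity rule, so it treats a laboratory-only finding as possible toxicity. In 7.4 itself the general grade 0 refers to normal limits. Both sit badly with a blanket laboratory exclusion.

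**Step 4. Ask whether the SAP recovers case C.** No SAP rule derives adverse events from laboratory data. SAP Tables 6.1.1 to 6.5 summarise laboratory results, but none is described as being by toxicity grade. Values remain visible in the listings, and the general methods call for minimum and maximum. What is missing is a count of patients by severity grade.

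**Step 5. Scale, as illustration only.** Input: n = 21, the first-stage size per group (Protocol 5.5).

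- Effect of one omitted patient on an incidence: 1/21 = 0.048, or 4.8 percentage points.
- The documents give no rate q of symptom-free grade 3-4 laboratory abnormality per patient. With assumed values, expected patients = 21q and chance of at least one = 1 − (1 − q)^21:

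| Assumed q | Expected patients of 21 | Chance of at least one |
|---|---|---|
| 2% | 0.4 | 35% |
| 5% | 1.1 | 66% |
| 10% | 2.1 | 89% |
| 20% | 4.2 | 99% |

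These are chances that a case C event occurs, not that it is omitted. Omission also requires the site to follow 7.4.

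**The case against.** The strongest reply is that 5.4 already captures these events. It collects what laboratory tests detect and grades by CTC AE 3.0, and nothing ranks 7.4 above it. A reader might infer that 5.4 limits recording to symptomatic laboratory values. It does not: the sentence on values with symptoms says where those are recorded and is silent on the rest. This part of the reply stands, and it reduces the consequence from certain loss to inconsistent recording.

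A second reply is that little is hidden. Symptomatic abnormalities and diagnosed syndromes are still reported, and all laboratory data are listed by subject and by parameter. This also stands, except that a listing is not a count by grade.

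A reader might further infer that the shift tables treat a grade 1 and a grade 4 value alike. That would hold only if their categories follow the normal range. The SAP leaves the categories undefined, so shifts by grade are not excluded.

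Finally, the SAP may rest on a later protocol. It cites item C of Protocol 2.2.7, which has no such item here, and its schedule includes pharmacokinetic and HAHA samples that are absent from this protocol's schedule. Whether the 7.4 exclusion governed the data under analysis therefore cannot be confirmed. That is a reason to check the version in force; it does not resolve the conflict in the text provided.

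**Conclusion.** The contradiction between 5.4 and 7.4 is real, 7.1 adds to it, and the SAP does not repair it. Recording of isolated, symptom-free grade 3-4 laboratory abnormalities may be inconsistent, and the grade 3 or above and serious adverse event tables can under-count them.

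The conclusion assumes that at least some sites or staff followed 7.4. Its size cannot be stated. The 4.8 points per omitted patient applies if a group has 21 patients, and the rates in the table are assumptions.

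Three stronger readings are not supported:

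- That severe laboratory toxicity as a whole vanishes from every adverse event table: cases A and B still enter.
- That the immune-related tables are certainly biased downward: Protocol 3.3.1 defines an autoimmune reaction by compromised organ function, and a diagnosed condition of that kind would be reported.
- That 42 patients were treated, as two full first stages would suggest: the SAP reports no response in the first stage and termination, but gives no treated count.

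**What to change.** **Protocol.** Use one adverse event definition in 5.4 and 7.4: remove the blanket laboratory exclusion and state when a laboratory abnormality counts. Use one definition of a serious event in 5.4 and 7.1. The grade-based rules in 3.3.1 and 4.4 depend on the same terms and must be reconciled with the result. The edit is short, but the trial has been terminated and forms may already be complete, so it may recover nothing already missed.

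**SAP 5.9.3 (the practicable change).** Derive CTC AE 3.0 grades from the laboratory values already collected. Make shift Tables 6.1.2 (hematology) and 6.2.2 (biochemistry) by grade, and add a table of worst post-baseline grade by group. A note to the adverse event tables should say that laboratory abnormalities may have been recorded inconsistently and point to these tables.

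**Cost.** Modest programming and no new data collection.
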